### **Pre-drug baseline study visits (Visits 1- 4)**

#### **Visit 1**

Participants will be encouraged to have a light meal prior to arrival.

1. Interval history, vital signs, and a brief physical exam.
2. Exercise testing:
  - a. **Cardiopulmonary Exercise Testing (CPET)**: A symptom-limited (maximal) graded cycle ergometer exercise test in association with air-gas-exchange, an optimal gauge of aerobic capacity will be conducted by trained research exercise physiologists. A study clinician will be immediately available if needed. A computerized cycle ergometer will be used to generate a symptom-limited exercise stimulus. ACSM criteria for starting and stopping will also be utilized. A face mask or mouthpiece will be positioned over the subject's mouth and nose during the exercise for gas exchange assessments. VO2, minute ventilation (VE)/exhaled carbon dioxide (VCO2) slope, and respiratory exchange ratio (RER) will be measured as well as hemodynamics (max HR and BP), time, and ECG waveforms). Any unexpected abnormalities will be reported to the participant's primary provider(s); continued participation in the study will require the primary provider's clearance. The rate of perceived exertion (RPE) will be completed during the CPET.
  - b. **400-meter corridor walk**: Participants will walk over a 400-meter course. During the 400-meter corridor walk, average VO2 per lap during steady-state

(2 minutes of plateaued  $\text{VO}_2$ ) will be used to calculate the energy cost of walking by normalizing the  $\text{VO}_2$  to lap gait speed (ml/kg/m).

- c. For participants with diabetes, they will be asked to bring their own glucometer to assess glucose before and after the CPET.
- d. **NIRS**: NIRS will be worn during the CPET and 400-meter corridor walk. Sensors will be placed on the skin of one leg to allow the non-ionizing, LED light source to assess tissue oxygenation and perfusion via measurements of the optical absorption of hemoglobin.
- e. **Accelerometry**: An ActiGraph wrist accelerometer will be worn during the 400-meter corridor walk to establish baseline activity parameters and during the CPET.

3. A battery of questionnaires will be administered.
  - a. The following questionnaires will be administered:
  - b. Community Healthy Activities Program for Seniors (CHAMPS)
  - c. Fried Frailty Index
  - d. EuroQol
  - e. Montreal Cognitive Assessment
  - f. Patient Health Questionnaire (PHQ-2)
  - g. PROMIS-Sleep Disturbance Short Form  
(<https://www.ncbi.nlm.nih.gov/pmc/articles/PMC3261577/>)
  - h. Self-efficacy: Sullivan
4. Participants who fail to meet applicable inclusion/exclusion criteria based upon the results of the screening assessment will be excluded from further study participation. Such participants will be paid for the visit.
5. Prior to departing, participants will be reminded to resume their usual medication regimen and clarify any modifications related to the study if indicated.

## Visit 2

Participants will be encouraged to eat a light breakfast prior to arrival.

1. Interval history, vital signs, and a brief physical exam.
2. Steady-State Walking Test: A steady-state walking (1.5 mph) test will be completed on a treadmill. Participants will wear a portable CPET device during the steady-state walk. The rate of perceived exertion (RPE) will be completed during the steady-state walking test.
3. Submaximal CPET: the participant will pedal on a cycle ergometer with a fixed resistance (the resistance associated with 60%-80% peak  $\text{VO}_2$  achieved during the initial symptom-limited CPET on visit one). The rate of perceived exertion (RPE) will be completed during the submaximal CPET.
4. Handgrip Strength Assessment
5. Short Physical Performance Battery (SPPB) will be completed:
  - a. Sitting and standing out of a chair

- b. Walking over a 4-meter course (to measure walking speed)
  - c. Standing with their feet in different positions to measure their balance
6. NIRS will be worn during the submaximal CPET. NIRS and ActiGraph will be worn during the steady-state walk.
7. Standard breath-by-breath CPET ventilatory indices  $VO_2$ ,  $VE/VCO_2$ , and RER will be collected and used to characterize the performance during the submaximal CPET as well as the steady-state treadmill walk completed in this study visit.
8. Three-day food record (3DFR): participants will be provided forms to complete a 3DFR which will be analyzed for plant-based dietary nitrite and nitrate. Participants will be assigned dates for these self-assessments, including one weekend day. Participants will be asked to maintain a diet that is consistent throughout the trial. Major dietary modifications during the 16-week trial will be discouraged.
9. Prior to departing, we will remind diabetic participants to resume their usual medication regimen and clarify any modifications related to the study if indicated.

### Visit 3

Participants will be encouraged to eat a light breakfast prior to arrival.

1. Vital signs will be completed by study or MRRC staff. Any concern for medical instability after collecting the vital signs and the interval history will prompt contact with a study clinician, and possible physical exam before proceeding.
2. Magnetic Resonance Spectroscopy (MRS):  
MRS is an in-vivo test to measure maximal mitochondrial capacity to generate ATP. It will be performed on the subject's leg as they complete a flexion-extension exercise within the bore of the magnet as described below.  
Prior to the exercise, the technician will collect a fully relaxed, high-resolution  $^{31}P$  spectrum image of the resting muscle.  
The exercise protocol will then be performed: Participants lay supine with the non-dominant knee (unless contraindicated) elevated at  $\sim 30^\circ$  and straps are placed over the legs. Participants perform voluntary isometric contractions (kicking) repeatedly as hard and as fast as they can for two bouts each followed by a rest period. The protocol is designed to deplete PCR stores by 33-66% to ensure high signal to noise defining PCR recovery without inducing acidosis ( $pH < 6.8$ ), which inhibits oxidative phosphorylation.
3. Participant may complete any remaining functional testing from Visit(s) 1 or 2. Visit 3 and Visit 8 will not occur if the Subject is ineligible for the MRS.

### Visit 4

Participants will be asked to fast for at least 8 hours prior to arrival.

Participants will be asked to hold their medications per the Anti-coagulation Medications Hold Plan.

1. Interval history, vital signs, and a brief physical exam

2. Staff will obtain verbal confirmation from participants of fasting for at least 8 hours prior to arrival and that Anti-coagulation Medications Hold Plan was followed.
3. An IV line will be placed
4. Skeletal Muscle Biopsy #1: Participants will lie comfortably in the supine position for biopsy of the vastus lateralis muscle of the non-dominant leg. Biopsy sites will be disinfected with chlorhexidine, lidocaine will then be administered to biopsy site. The physician investigator or study clinician will then make a small incision in the skin and insert a needle into the vastus lateralis to remove approximately 150 mg of muscle. Additional passes of the needle may be necessary for an adequate muscle sample. The wound site will be closed with Steri-strips™ (or a suture if subject is allergic to Steri-strips™) and a sterile pressure bandage.
  - a. Muscle specimens will be immediately processed and stored. Muscle specimens will be divided into portions for specific analyses. Any extra tissue will be stored for future analyses.
  - b. The biopsy wound will be compressed and dressed.
5. Randomization: Subject will be randomized following review of the participant safety status by PI.
6. Pharmacokinetics (pK)
  - a. Nursing staff will measure BP, RR, HR, SpO2, and MetHb to ensure subject is at a steady-state before administering the study drug. Baseline assessments of nitrite/nitrate will be collected. Participants will receive their first dose of study drug (20 mg Nitrite vs. Placebo). Then, the following will be assessed: BP(orthostatic hypotension assessment), HR and MetHb, RR and SpO2 every 15 minutes for the 2 hours post-drug administration period per standard operating procedure. If high MetHb level or if subject is hypotensive or symptomatic, after the study drug is administered, the PI or study clinician will be informed and advise on plan for management.
7. Blood assessments:
  - a. Nitrite/Nitrate Serum Levels and other Research Bloods: baseline (before study drug), 30 minutes, 60 minutes
  - b. Platelet Mitochondrial Respirometry: baseline (before study drug), 30 minutes
  - c. Research Inflammatory Indices: baseline (before study drug)
  - d. Heparinized blood will be immediately centrifuged at bedside to separate plasma and red cells and then flash frozen for future analyses. Total volume of blood drawn for 3 samples will be about 80 ml (about 5.4 tablespoons).
8. Skeletal Muscle Biopsy #2 immediately after the 30-minute blood sample is drawn.
9. A breakfast will be provided after the skeletal muscle biopsy #2.
10. If the study drug is well tolerated, the PI will be contacted and IDS orders for enough study drug/placebo will be ordered to sufficiently cover dosing for participants as described in drug distribution section.
11. Drug supply dispersal

- a. Participants will receive sufficient study drug/placebo supply. We will instruct participants to return all of the study drug packaging, including unused study drug and empty packaging at each study visit and/or at the time of discontinuation from treatment.
12. Study staff will review medication administration and use of the drug diary card with all participants. Participants will be asked to record the time they take the drug each day and any symptoms with severity rating and/or health events during the dosing period.
13. The study staff will review biopsy site care with participants and if indicated, remind participants to resume their normal anti-coagulation/anti-platelet/anti-diabetic medications.
14. Participants will be called 2 days after biopsy for assessment of biopsy healing. All participants will be given the option of returning for an Interim Visit for direct assessment if symptomatic.
15. Daily activity: Participants will be encouraged to begin or extend a daily walking routine with specific instructions and encouragement to progress in time and length as tolerated.

In order to track these changes over the course of the 12-week intervention, participants will be asked general questions about activity level, exertion level, and barriers to activity. Furthermore, the study nurse will ask about any progress as part of the interim study on-site and phone-based assessments.

The Daily Activity questions are not a study endpoint, but rather they are pragmatic tools to encourage motivation and behaviors of activity. Only the ActiGraph data are study endpoints.

### **Midway Drug Intervention Assessment (Visit 5)**

**Visit 5 (Midway):** On-site assessment to assess safety and abbreviated functional assessment during the 12-week intervention phase. Participants will be asked to fast for at least 8 hours prior to arrival.

The following procedures and assessments will be completed:

1. Interval history, vital signs, and a brief physical exam.
2. IV line will be placed
3. Dose Monitoring:
  - a. Subject will take morning dose of study drug
  - b. Research Blood assessments at baseline (before study drug), 30 minutes, 60 minutes:
    - i. Nitrite/Nitrate Serum Levels and other Research Bloods: baseline, 30 minutes, 60 minutes
    - ii. Platelet Mitochondrial Respirometry: baseline (before study drug), 30 minutes
    - iii. Research Inflammatory Indices: baseline (before study drug)
    - iv. CBC (for safety assessment)
4. pK assessments as in Visit 4 with orthostatic hypotension assessment Blood Pressures.
5. Functional evaluation:
  - a. Participants will complete the following:

- i. Steady-state walk, 400-meter corridor walk (with VO2 assessment), SPPB, Handgrip Strength
- ii. Participants will complete the Steady-state walk test 30minutes(+/-10 minutes from the 30 minute blood collection)
6. Additional study drug capsules distributed if needed
7. A breakfast will be provided after the 60-minute blood draw
8. 7-Day Home Activity Monitoring

### **Post-Drug Assessments (Visits 6-9)**

The procedures and assessments are generally similar to those performed Pre-drug baseline study visits.

#### **Visit 6**

Participants will be encouraged to have a light meal before arrival. Participants will be asked to hold their AM study drug prior to arrival.

See Visit 1 for details.

Study staff will update concomitant medication list and complete a symptom assessment. The drug diary cards and empty drug boxes for completed weeks on study drug/placebo will be collected. Compliance of the study drug will be reviewed.

1. Interval History, vital signs, and a brief physical exam.
2. The participant will take their study drug 30 minutes before the CPET.
3. Cycle Ergometer symptom-limited CPET
4. 400-meter corridor walk
5. Questionnaires
6. Prior to departing, we will remind diabetic participants to resume their usual medication regimen and clarify any modifications related to the study.
7. Blood work collected by trained study staff. (See Study Timeline 2.2.2)
8. Prior to departing, we will remind diabetic participants to resume their usual medication regimen and clarify any modifications related to the study if indicated.

#### **Visit 7**

Participants will be encouraged to eat a light breakfast prior to arrival. The participants will be asked to take their study drug 30 minutes prior to the submaximal CPET.

Interval history, vital signs, and a brief physical exam.

See visit 2 for details.

1. Steady-State Walking Test
2. Submaximal CPET
3. Handgrip Strength Assessment.

4. SPPB
5. 3DFR will be provided to subject and collected at following visit.
6. Prior to departing, we will remind diabetic participants to resume their usual medication regimen and clarify any modifications related to the study if indicated.

## Visit 8

Participants will be encouraged to eat a light breakfast prior to arrival. The participant will be asked to hold the AM dose of the study drug prior to arrival. The participant will take the study drug ~30 minutes prior to start of the MRS.

See Visit 3 details.

1. MRRC Staff will collect vital signs. Any concern for medical instability after collecting the vital signs and the interval history will prompt contact with a study clinician, and possible physical exam before proceeding.
2. MRS
3. Participant may complete any remaining functional testing from Visit(s) 6 or 7
4. Participant will take the afternoon dose of study drug 30 minutes prior to completing any remaining functional testing from visit 7.

## Visit 9

Participants will be asked to fast for at least 8 hours prior to arrival. Participants will be asked to hold their AM dose of the study drug prior to arrival.

See Visit 4 for details.

1. Interval history, vital signs, and a brief physical exam.
2. Staff will also confirm participant has been fasting for at least 8 hours prior to arrival and that any customary anti-platelet or anti-coagulation medications were held as instructed.
3. An IV line will be placed
4. Skeletal Muscle Biopsy #1
5. Participant will self-administer AM dose of study drug.
6. Research Blood assessments at baseline (before study drug), 30 minutes, 60 minutes, as per Pre drug biopsy visit.
7. Skeletal Muscle Biopsy #2 immediately after the 30-minute blood sample is drawn.
8. Pharmacokinetics (pK) with orthostatic hypotension assessment Blood Pressures every 15 minutes as noted in Visit 4.
9. A breakfast will be provided after the second skeletal muscle biopsy.
10. Remaining study drug/placebo, 3DFR, daily activity questions, drug diary cards, and/or Actigraphy and diary will be collected from subject prior to discharge.
11. Participants will be called 2 days after biopsy for assessment of biopsy healing. All participants will be given the option of returning for an Interim Visit if they prefer a direct assessment.

12. The study staff will review biopsy site care with participants and if indicated, remind participants to resume their normal anti-coagulation/anti-platelet/anti-diabetic medications
13. Following safety monitoring the study staff will schedule final follow up phone call for 1 week after visit 9.

### **Weekly Telephone Calls**

Following Visit 4, the study staff will contact participants by phone each week to review any symptoms. Staff will continue to call weekly until 1 week after visit 9. Each call will last approximately 5-10 minutes. We will ask participants if they have missed any study drug doses and if there have been any changes in their medications or medical history, including emergency room visits or hospitalizations since their study visit. We will ask participants to review their drug diary card to report what they wrote down for the week to help them remember.

We will also remind participants to contact the study staff or doctor anytime their health care team suggests a change in medications or if they have any symptoms that cause concern. There will be study personnel available to address participant's questions or concerns 24 hours/7 days a week.

During the drug intervention period, participants will also be asked about their activity levels, exertion levels, activity enjoyment, and barriers to activity as part of the weekly calls.

## 2.2.2 Study Timetable

Study Phase	Pre-Drug Assessments					Midway Assessment	Post-Drug Assessments			
	Consent Visit	Visit 1	Visit 2	Visit 3	Visit 4		Visit 6	Visit 7	Visit 8	Visit 9
Approximate Time between Study Visits		Same day to +30 days	Visit 1 +1 day to ±14 days	Same day to +7 days	Previous Visit +1 day to ±14 days	6 weeks ±5 days	6 weeks ±5 days	Visit 6 days ±14 days	Same day to +7 days	Previous Visit to ±14days
Approximate Duration of each visit	1-2 hours	3-5 hours	3-4 hours	1-2 hours	3-4 hours	1-2 hours	3-4 hours	3-4 hours	1-2 hours	3-4 hours
Fasting prior to arrival					X	X				X
Consent	X									
Medical History	X									
Physical exam	X	X	X	X **	X	X	X	X	X **	X
Vital Signs	X	X	X	X						
Vital Signs with Methemoglobin					X	X	X	X	X	X
Max CPET*		X					X			
Sub-Max CPET*			X					X		
400-Meter Corridor Walk*#		X				X	X			
Steady-state walk*#			X			X		X		
SPPB			X			X		X		
Handgrip			X			X		X		
Home Actigraph	X	*					X			
Questionnaires	X	X					X			

3 Day Food Record (3DFR)**			X					X		
MRS				X					X	
Randomization					X					
Muscle Biopsies 1 & 2					X					X
Blood Draw Approximate total quantity	20 ml+				83 ml	81 ml	20 mL			81 ml
CBC	X+					X	X			
Complete Metabolic Panel (CMP)	X+						X			
25-hydroxy vitamin d (Vitamin D)	X+						X			
HbA1c	X+						X			
TSH	X+									
Nitrite/Nitrate					X	X				X
Inflammatory Indices					X	X				X
Additional Research Bloods					X	X				X

\*Assessment with NIRS

#Assessment with ActiGraph

+ Blood draw may be collected after signing consent and before randomization, blood draw may not include CMP and/or CBC/d if collected within the last 4 weeks

++ 3 Day Food Record distributed at Visit 1 and Visit 6 and collected from subject at Visit 2 and Visit 7

++ If deemed necessary

## **2.3 STUDY DRUG**

[name] has developed nitrite capsules for oral dosing prepared using 14-nitrogen formulation in collaboration with the University of Iowa's drug development program and FDA approved under IND 115,926. Greater than 99.9% of naturally occurring nitrite exists as 14N nitrite.

### **2.3.1. Study Drug Preparation and Dispensing**

The institutional Investigational Drug Service (IDS) pharmacy at the University of Pittsburgh will select study drug/placebo by the randomization sequence number. The independent research pharmacist at IDS will package all drugs/placebos to be similar in physical appearance. The study drugs are oral formulation of 20 mg sodium nitrite and matching placebo. Sodium nitrite of dose strengths and matching placebo will be supplied as capsules for oral administration. All capsule formulations will be identical in appearance (size, shape, color) and smell. The packaging and labeling will be designed to maintain blinding to the Investigator's team and to participants.

### **2.3.2. Drug Administration**

IDS will be provided an updated order for dispensing drug/placebo at baseline and PRN. Participant will be instructed to bring remaining supply to follow up visit for interim monitoring counts.

#### **2.3.4. Treatment Period**

Participants will undergo study drug treatment duration of up to 16 weeks of nitrite vs. placebo three times daily; study drug during the 12 week intervention period and over the 2-4 week post intervention period. The two to four additional weeks during post intervention period are included to:

- allow continuation of the study drug/placebo through the final outcome collection series of visits
- Range of two to four post intervention weeks accounts for minimum length of time between Visits 6 and Visits 9 and the maximum length of time allowed between Visit 6 through Visit 9.

This is considered appropriate to study benefits of oral nitrite therapy.

#### **2.3.5. Breaking the Blind**

All participants and study personnel (except the study statistician, the dedicated providers, our safety officer and the study adjudicator) involved in assessments will be blind to treatment assignment.

#### **2.3.6. Medication Compliance**

At Visit 4, participants will self-administer their first dose of study medication under the supervision of the physician investigator or study clinician in the outpatient facility following completion of all baseline clinic assessments. After the pK (and participant is stable after first dose), participants will be dispensed their study medication for home use in prefilled seven-day labelled pill boxes to help with compliance and to help reduce burden or confusion. On the weekly phone calls, the study coordinator will review the daily diary card (study drug and symptoms), inquire about missed doses and review symptom assessments. Participants will return empty pill boxes when they return for study visits. Medication adherence will be reviewed. Participants will return any remaining capsules at their Visit 9 for final accountability. In the event that the adherence rate is <80% at any time reported by the subject, participants will be re-educated on medication adherence. If medication compliance repeatedly falls outside of the acceptable range, the study investigators will discuss subject eligibility for continued participation in the study. Of note, adherence during [name] pilot study was excellent with no subject approaching the 80% level of concern.

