### **2.4.2 Data Analysis**

Overview: All statistical analyses will be performed and overseen by the study statistician [name] (see LOS) using SAS® version 9 (SAS Institute, Inc., Cary, North Carolina). Participant

flow will be summarized using a CONSORT diagram. Data will be summarized by intervention arm and time point as well as baseline to follow-up change using appropriate descriptive statistics. First, the baseline participant characteristics will be compared between the two arms. Any significant differences will be noted and accounted for as additional covariates in the sensitivity analyses. Second, main analyses to address the aims will be performed as outlined below using multiple imputation for missing data. The primary analysis will be performed to test the primary hypotheses H1a about the primary outcome of mitochondrial respiration (high resolution respirometry). Secondary analyses will be performed for remaining hypotheses, secondary outcomes and other exploratory analyses. Third, we describe below our primary approach to missing data and a set of sensitivity analyses by including additional covariates and ignoring missing data.

**Baseline Comparison:** Due to the adaptive randomization scheme, it is unlikely that baseline participant characteristics will be significantly different between the arms. If we do find any, they will be included as additional covariates in the sensitivity analyses. We will not alter the primary analytic strategy to preserve its a priori nature and predictability. We will use independent samples t- or Wilcoxon rank sum tests, as appropriate based on distributional properties, to compare continuous baseline characteristics between the intervention arms. For categorical baseline participant characteristics, we will use chi-square and Fisher's exact tests, as appropriate. Statistical significance of the intervention term will be interpreted as indicating the need to include them as covariates in sensitivity analyses.

**Aim 1 Analysis:** Analysis of covariance (ANCOVA) model using the SAS® GLM procedure with baseline to follow-up change in mitochondrial respiration (high resolution respirometry) as the dependent variable, intervention arm (nitrite/placebo) as the effect of main interest, and the baseline value of mitochondrial bioenergetics as a covariate. The magnitude and statistical significance at  $\alpha=0.05$  of the nitrite vs placebo contrast will serve as the formal test of the primary hypothesis H1a.

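### Repeated poor compliance can, at the investigators' discretion, end a randomised participant's time in the study before the Visit 9 biopsy, and no text keeps the outcome or defines an all-randomised analysis

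*Combined protocol and SAP*

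**What the plan says.** Section 2.3.6 sets out two steps. The first concerns reported intake: "In the event that the adherence rate is <80% at any time reported by the subject, participants will be re-educated on medication adherence". The second concerns the participant's place in the trial: "If medication compliance repeatedly falls outside of the acceptable range, the study investigators will discuss subject eligibility for continued participation in the study". The 80% self-report figure belongs to the first step only. The second step refers to a range that is not given a number and is not tied to self-report. The section then adds that "adherence during [name] pilot study was excellent with no subject approaching the 80% level of concern".

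Capsule information is collected as well. Section 2.3.2 states: "Participant will be instructed to bring remaining supply to follow up visit for interim monitoring counts". Visit 4 asks for unused drug and empty packaging to be returned, Section 2.3.6 has remaining capsules returned at Visit 9, and Section 2.3.7 records amounts dispensed and returned.

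On timing, Section 2.2.1 places randomisation at Visit 4, after the first baseline biopsy: "Subject will be randomized following review of the participant safety status by PI". The timetable in Section 2.2.2 shows muscle biopsies at Visits 4 and 9 only.

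On analysis, Section 2.4.2 specifies an ANCOVA "with baseline to follow-up change in mitochondrial respiration (high resolution respirometry) as the dependent variable", with multiple imputation in the main analyses. Section 2.4.4 bases the imputation on missing at random with five imputations, and lists ignoring missing values and carrying the last value forward as sensitivity analyses.

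**The concern.** Adherence is behaviour after randomisation, and treatment can influence it through tolerability or perceived benefit. The second step in Section 2.3.6 is about participation in the study, not only about taking capsules. The plan has no route by which someone stops or largely stops study drug and still attends Visits 6 to 9. Where Section 10 deals with outpatient hypotension, it couples discontinuing with leaving the trial. There is no statement of an intention-to-treat principle and no definition of an analysis set.

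A participant removed under this sentence may therefore have no follow-up respiration value because of an investigator decision rather than their own unwillingness. If that happens, the primary contrast describes the effect in people who kept taking the capsules, while the reader will take it as the effect of being assigned to nitrite. Section 2.4.4 itself says prevention is the best way to handle missing data, and this sentence allows avoidable missing data to be created.

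**Working it through.** **1. The plan's own figure.** Inputs from Section 2.4.1: 35 randomised per arm, about 14% dropout, 30 completers per arm, SD of change 97.61 pmol/min/mg, two-sided α = 0.05, power 80%.

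- Completers: 70 × 0.86 = 60.2, i.e. 30 per arm.
- Two-sample t-test (noncentral t), 30 per arm: power at 71.80 is 0.800, and the detectable difference at 80% power is 71.80.
- Effect size: 71.80 / 97.61 = 0.736, stated as 0.74.

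The stated sample size reproduces.

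**2. How far the estimate could move.** The documents give no rate of repeated poor compliance in this trial and no effect in poor compliers, so both are assumed. Let 71.8 be the effect in adherers, p the share of the nitrite arm removed, and q the fraction of the effect those people would have had.

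- Effect of assignment = 71.8 × [1 − p(1 − q)]
- Estimate if they are removed and imputed from those who stayed ≈ 71.8
- Overstatement = 1 / [1 − p(1 − q)] − 1

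| Removed (p) | Half the effect (q = 0.5) | No effect (q = 0) |
|---|---|---|
| 0 | 71.8; 0% | 71.8; 0% |
| 1 in 35 (2.9%) | 70.8; 1.4% | 69.7; 2.9% |
| 5% | 70.0; 2.6% | 68.2; 5.3% |
| 10% | 68.2; 5.3% | 64.6; 11.1% |
| 15% | 66.4; 8.1% | 61.0; 17.6% |

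For scale, the standard error of the difference with 30 per arm is 97.61 × √(2/30) = 25.2. The largest shift in the table, 71.8 − 61.0 = 10.8, is 0.43 of that. One removal with no effect, 71.8 − 69.7 = 2.1, is 0.08 of it.

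**3. Whether the planned imputation corrects this.** Simulation: 30 per arm; ANCOVA on change with baseline as covariate; five imputations from arm and baseline; 10% poor compliers in each arm with no benefit and no other difference in prognosis; 6,000 repetitions. The mean estimates were:

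- everyone kept with an outcome: 64.8
- poor compliers removed, complete cases: 72.0
- poor compliers removed, multiple imputation: 72.0

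The small gap between 72.0 and 71.8 is simulation error. Imputation gives the same answer as ignoring the missing values, because the model learns only from those who stayed. Carrying a value forward does not recover the outcome either, since the only earlier muscle respiration values are those from Visit 4.

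**4. Power.** If removals came on top of the planned dropout, power at 71.8 would be 78.6% with one more lost per arm (detectable difference 73.1) and 75.6% with three more (75.8). Up to 5 of 35 per arm (14.3%) may already be covered by the 14% allowance, in which case nothing further is lost.

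Keeping poor compliers does not restore power in general. With 10% poor compliers and 30 completers per arm, power is 71.3% if they are kept and have no effect, 75.8% if they are kept with half the effect, and 75.6% if they are removed. The argument for keeping them concerns what is estimated, not power.

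**The case against.** **The events may be rare.** The pilot statement is in the same section, and the plan offers no reason to expect 10 or 15% removals. Someone repeatedly just below 80% still takes most capsules, so assuming no effect is extreme. This stands, and it is why the range starts at zero.

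**Removal is not prescribed.** The text says only that "the study investigators will discuss subject eligibility for continued participation in the study". A reader might infer that reporting less than 80% leads to removal. It does not: that figure leads to re-education. A reader might also infer that the plan penalises honest reporting. The second step is not restricted to self-report, and capsule counts are collected, so the documents do not support that either. The undefined range remains a gap.

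**The comparison is still protected to a large degree.** Participants and most assessment personnel are blind (Sections 2.3.5 and 2.3.10), and one rule applies to both arms. To say that randomisation no longer protects the comparison would go beyond the documents. Removal could differ by arm through tolerability, but nothing in the plan indicates how much.

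**A proof-of-mechanism trial may want the effect under adequate exposure.** That is a legitimate question, but the plan does not say it is the one being asked. Keeping the outcomes permits both analyses; losing them rules out an observed all-randomised comparison.

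**Conclusion.** The concern holds in a limited form. Section 2.3.6 permits, and does not require, ending a randomised participant's participation for repeated compliance outside an undefined range. It is an inference, though a natural one, that such a participant would miss the Visit 9 biopsy: the plan provides no other route. If so, none of the planned missing-data methods recovers the outcome, and the estimate moves toward the effect in adherers.

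The size cannot be derived from the documents. On the stated assumptions, the overstatement runs from 0 to about 18%, with about 1 to 3% for a single removal in 35. These figures rest on a true effect of 71.8 in adherers, no prognostic difference between poor compliers and others, and an imputation model that does not use adherence (none is named). The losses may already lie within the planned 14% dropout. A reader might infer that the sample size is wrong; it is not. This is a cheap improvement worth making, not a fault that invalidates the design.

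**What to change.** Amend Section 2.3.6 along these lines: *Low adherence alone leads to re-education and is documented. It does not end outcome collection. Visits 5 to 9, including the Visit 9 biopsy, are still sought from every participant willing to attend.*

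Add to Section 2.4.2: *All randomised participants are included in the primary analysis in the arm to which they were assigned. Adherence is used only in a supplementary analysis.*

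State how adherence is calculated, basing it on the capsule counts already collected, with diary and telephone reports as support, and define or delete the acceptable range.

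Safety decisions under Section 10 and voluntary withdrawal are unchanged. The amendment concerns outcome collection and takes no position on whether study drug is continued.

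The cost is a few sentences. The visits are already in the schedule and the payment table. The downside is some dilution of the estimate by poor compliers who are kept; if they are as rare as the pilot suggests, this will be slight.
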